9.3.2 Secondary analyses

In a second analysis we will calculate the incidence rate ratio of leprosy at village level between arms 1 and 2. Here all participants enrolled will be taken into account, even those that did not receive PEP. A similar model as in the primary analysis will be used, including all persons in the villages randomized, even those who were not eligible to receive the study treatment due to age or weight restrictions.

Prespecified adverse events such as gastro-intestinal (nausea, vomiting), nervous system-related (headache, dizziness) and cutaneous reactions will be tabulated and presented using counts and percentages. Comparisons between study arms will be done using Fisher's exact test.

In the villages that were originally allocated to arm 4 of the PEOPLE trial, the fourth and final screening round will be accompanied by one final anti-PGL1 sero-survey. Based on the comparison of age specific anti-PGL-I sero-prevalence rates at the time of the 2019 survey and in the final survey in 2026, we will assess the potential of anti-PGL-I surveys as a tool to monitor leprosy transmission. We will compare seroprevalence rates in different age groups of 2019 to 2026, both overall and by village and island to assess whether a trend can be identified and whether this trend is consistent across villages/islands. This analysis will be primarily descriptive.

Cost data will be gathered throughout the study and used to calculate the average cost per person screened for leprosy by island, average cost per case detected by island. If BE-PEP is shown to be more effective than SDR-PEP, a cost-effectiveness analysis will be done estimating the average cost per case of leprosy averted by study arm and by island. Incremental costs will be calculated using the SDR-PEP arm (arm 2) as baseline.

Prevalence of bedaquiline and/or rifampicin resistant strains will be calculated per island with in the numerator all leprosy patients with rifampicin or bedaquiline resistant isolates identified and in the denominator all patients tested. Along with the proportions 95% confidence intervals using the Wilson's method will be calculated.

Results of genotyping of *M.leprae* will be analyzed separately in the framework of the project titled: 'Improving leprosy prevention strategies by integrating social network analysis with spatial and molecular epidemiology data of *Mycobacterium leprae* in the Comoros'.

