2.2.2 Secondary

1. To assess effectiveness of the BE-PEP regimen at village level.

Outcome: The incidence rate ratio between villages that received BE-PEP and villages that received SDR-PEP.

2. To quantify frequency of potential adverse events such as gastro-intestinal (nausea, vomiting), nervous system-related (headache, dizziness) and cutaneous reactions.

Outcome: The proportion of participants treated with BE-PEP that report adverse events, with a breakdown by type of event.

3. To assess anti-PGL-I sero surveys as a tool to monitor leprosy transmission

Outcome: Age specific anti-PGL-I sero prevalence rates in villages belonging to arm 4 of the original PEOPLE trial at the time of the first survey round in 2019 and the final round of BE-PEOPLE in 2026

4. To monitor rifampicin and bedaquiline resistance among leprosy and tuberculosis patients

Outcome: We will quantify the prevalence of rifampicin and/or bedaquiline resistant strains of *M. leprae* and *M. tuberculosis* on each of the study islands making use of molecular markers.

5. To assess cost-effectiveness of the BE-PEP regimen compared to SDR-PEP.

Outcome: Cost per case averted between BE-PEP arm and SDR-PEP.

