Year 2	Phase 3 study	Screening Arm 1 & 2 + PEP intervention	Sampling leprosy patients	Sampling TB patients	
Year 3	Phase 3 study	Screening Arm 1 & 2 + PEP intervention	Sampling leprosy patients	Sampling TB patients	
Year 4	Phase 3 study	Final screening Arm 1 & 2	Sampling leprosy patients		PGL-I survey

Table 1: Time table BE-PEOPLE

Participants in the new villages will be asked for informed consent for baseline screening in 2022. Informed consent for the phase 3 intervention trial will be asked during the first intervention round in 2023, when we know to which study-arm villages have been randomized. Informed consent for the leprosy patient cohort will remain separate, the same applies to the TB patients being enrolled. For the PGL-I survey in 2026, separate informed consent will be asked ahead of the survey.

Figure 1 below shows how villages belonging to the various arms of PEOPLE will merge into BE-PEOPLE. We have dropped some villages that had a low incidence so far during the PEOPLE trial or a small population size. To arrive at the required sample size we will also include nine new villages, eight on Anjouan and one on Mohéli, the latter to be split into two clusters. Villages will be arranged by PEOPLE study arm and by island in order of decreasing prevalence during the 2022 baseline survey and regrouped into pairs. Within each pair they will be randomized to arm 1 or arm 2 of BE-PEOPLE.

[figure not shown]

Figure 1: Inclusion and randomization BE-PEOPLE (Phase 3) trial

The main outcome measure of BE-PEOPLE will be the incidence rate ratio of leprosy between individuals in arm 1 who received BE-PEP and individuals in arm 2 who received SDR-PEP, controlled for potential confounding by distance to nearest index case at baseline, as well as for contextual confounding through the use of a random effects model (village nested within island). To avoid a potential selection bias, those who received SDR-PEP but would not have been eligible for BE-PEP, i.e. children below the age of 5 or with a weight below 20 kg, will be excluded from this analysis. Details are described in chapter 9, 'Data analysis'.

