4.4 Randomization

For the phase 2 safety study we will first complete the final survey round of the PEOPLE study and then enumerate all those aged 5 years or above, weighing 20 kg or above and not currently suffering from leprosy. They will be divided into three age categories, 5-12 years, 13-17 years, and 18 years and above. We will then determine the overall proportions of the three age groups, the proportion multiplied by 150 will be the number of participants to be recruited per study arm for each age group. Next we will prepare sealed envelopes containing a note indicating either BE-PEP or SDR-PEP as PEP regimen, 300 in total. They will be divided into three groups with equal numbers per PEP regimen, one group of envelopes for each of the three age categories.

The next step will be to enroll the required numbers of adults (age 18 years and above) by visiting the households one by one and inviting eligible subjects to be enrolled. Each time a person agrees, an envelope will be drawn and either SDR-PEP or BE-PEP will be provided as indicated on the note inside the envelope. This process will continue until all envelopes for adults have been allocated. Provided no concerning adverse events are observed, the procedure will be repeated for the 13-17 years old. Again if no concerning adverse events are observed, the 5-12 years old will be enrolled following the same procedure. The remainder of the village population aged 2 years and above and not meeting other exclusion criteria will then be offered SDR-PEP.

Randomization for study arms 1 and 2 of the phase 3 study, will take place upon completion of the baseline survey. We will then arrange all villages by island and by group (former arm 1, 2, 3 or 4 or new villages), in order of decreasing prevalence. As was explained earlier, Fomboni, the capital of Mohéli, will be split into two clusters. Thus we will arrive at 22 pairs of clusters. Blocked randomization will be used to allocate clusters into the two study arms. The randomization schedules will be prepared by an independent sponsor biostatistician. The randomization list will be prepared using SAS 9.4 (SAS Institute, Cary NC).

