7. SAFETY ASSESSMENT

7.1 Rationale for safety and efficacy of study drugs

7.1.1 Safety of Rifampicin 600mg

The regimen used for prophylaxis in arm 2, single dose Rifampicin, has been extensively tested in a number of leprosy PEP trials and is the current choice when PEP is implemented programmatically. In 2018 WHO issued a guideline for the diagnosis, treatment and prevention of leprosy which states that: 'Single-dose rifampicin (SDR) may be used as leprosy preventive treatment for contacts of leprosy patients (adults and children aged 2 years and above), after excluding leprosy and tuberculosis (TB) disease, and in the absence of other contraindications'.[34]

Indeed, in the first two years of the PEOPLE trial in which rifampicin was used at a dose of 1200 mg, no adverse events were identified related to the study medication. In BE-PEOPLE the WHO recommended dose of 600mg will be used as comparator arm, in order to test whether bedaquiline enhanced WHO recommended PEP is more effective at preventing leprosy.

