9.3. Phase3 study

9.3.1. Primary analysis

The main analysis will be to assess the effect of BE-PEP at individual level. Because in the first study year anyone living within 100 meter of an index case over the period 2018-2023 will be eligible for PEP and if this is more than 50% of the village population the entire village population above 2 years of age will be eligible where for the first year any leprosy case included in the study population detected

during the annual village screening or in the preceding five-year period, i.e. since January 1st, 2018 will be considered an index case. The following years, any leprosy case detected after the last year's screening up to and including the village's screening round of the current year will be considered an index case. Therefore, we assume that in the first year there will be blanket coverage with either SDR-PEP or BE-PEP. We will fit a Poisson model adjusted for follow-up time as an offset term with village nested in island as random effect and type of PEP (BE-PEP or SDR-PEP), as explanatory variable. Those who did not receive PEP and those below the age or weight limits for BE-PEP will be excluded from this analysis, SDR-PEP will be our reference category. Outcome variable will be incident leprosy. We will consider all cases diagnosed after the first intervention round in 2023, until the final survey in 2026.

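### Phase 3 adverse events are compared with Fisher's exact test on individuals although village clusters were randomized, so p-values are too small if reporting varies by village

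*Protocol*

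**What the plan says.** Protocol section 4.4 describes the phase 3 allocation: "Thus we will arrive at 22 pairs of clusters", and "Blocked randomization will be used to allocate clusters into the two study arms". Section 3.1 adds that pairs are formed by island, former PEOPLE arm and baseline leprosy prevalence: "Within each pair they will be randomized to arm 1 or arm 2 of BE-PEOPLE".

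The primary leprosy model in section 9.3.1 is a Poisson model "with village nested in island as random effect and type of PEP (BE-PEP or SDR-PEP), as explanatory variable", and section 9.3.2 uses a similar model for the village-level comparison. For AEs, section 9.3.2 says that gastro-intestinal, nervous-system and "cutaneous reactions will be tabulated and presented using counts and percentages", and then: "Comparisons between study arms will be done using Fisher's exact test". It names no village, island or pair term.

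The AE outcome in section 2.2.2 is "The proportion of participants treated with BE-PEP that report adverse events, with a breakdown by type of event", which is a description of one arm. The between-arm test appears only in section 9.3.2. Section 9 defers detail to a binding SAP, but the SAP supplied states in its introduction that it covers the phase 2 study.

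**The concern.** Fisher's exact test is right for phase 2, where individuals are randomized (section 9.2.2 specifies it there). In phase 3 the village is the unit of allocation, so between-village differences in AE reporting are part of the error in the arm comparison. A test on individuals leaves that part out.

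Such differences are plausible from the plan itself. AEs are self-reported at a home visit after dosing, and later events depend on participants or community health officers coming forward (section 7.2.3). Several field teams, organized by island, do the work (sections 3.1 and 4.1). Treatment is open label (section 5.1). How large the differences will be is unknown.

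At stake is the reading of the tolerability data. Section 7.2.3 counts the listed events as related to PEP when they occur within 24 hours, so a chance difference between villages could be taken for a drug effect. With no true difference, the error can also favour BE-PEP.

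**Working it through.** **1. The plan's own cluster calculation.** Inputs from section 4.3: control risk p0 = 0.0033, p1 = 0.00165 (50% reduction), m = 1,708 per cluster, between-cluster CV k = 0.4, power 90%, alpha 0.05 (two-sided assumed). The Hayes and Bennett formula is

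c = a + (1.960 + 1.282)² × [p0(1−p0)/m + p1(1−p1)/m + k²(p0² + p1²)] / (p0 − p1)²

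The three bracketed terms are 1.926×10⁻⁶, 0.964×10⁻⁶ and 2.178×10⁻⁶. Divided by 2.7225×10⁻⁶ and multiplied by 10.51, they give 19.56. With a = 2 (matched pairs) c = 21.56, so 22 per arm; with a = 1 (unmatched) it is 20.56, so 21. The stated 22 is reproduced in the matched form, and 44 × 1,708 = 75,152 agrees with the text. The between-village term is 2.178/5.068 = 43% of the bracket, so the plan treats village variation as important for leprosy.

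**2. Inputs for the AE test.** There are 22 clusters per arm (section 4.3). The mean size of 1,708 is the section 4.3 figure for PEP takers old and heavy enough for BE-PEP: 2,819 × 0.73 × 0.83 = 1,708. AE risk p and its between-village CV k are not given, so ranges are assumed. The value k = 0.4 is the plan's figure for leprosy, not for AEs.

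**3. Formulas.** ICC = k²p/(1−p). Design effect DE = 1 + (m−1) × ICC. False-positive rate of an individual-level test = 2[1 − Φ(1.96/√DE)].

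Example with p = 5%, k = 0.2: ICC = 0.04 × 0.05/0.95 = 0.00211; DE = 1 + 1,707 × 0.00211 = 4.59; 1.96/√4.59 = 0.915; rate = 36%.

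**4. Results with 1,708 per cluster and no true difference.** Each cell gives k = 0.1 / 0.2 / 0.4. The simulation drew beta-binomial clusters, 4,000 runs per cell.

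| AE risk | Formula | Fisher, simulated |
|---|---|---|
| 0.1% | 5 / 6 / 8% | 3.7 / 4.5 / 5.9% |
| 0.33% | 6 / 8 / 16% | 4.6 / 6.2 / 14.3% |
| 1% | 7 / 13 / 31% | 6.6 / 12.2 / 30.5% |
| 5% | 15 / 36 / 62% | 14.4 / 35.0 / 60.8% |
| 10% | 25 / 50 / 73% | 24.8 / 48.2 / 73.5% |

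DE runs from 1.02 (0.1%, k = 0.1) to 31.3 (10%, k = 0.4). With no village variation Fisher's test gave 3.8 to 5.9%, so the inflation comes from clustering. The formula overstates Fisher's error when events are few, because the exact test is then conservative; the simulated column is the one to use.

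**5. A cluster-level test on the same data.** A paired t-test over 22 pairs (21 df) gave 4.3 to 5.3% in all 15 cells. With unequal cluster sizes (size CV 0.6, assumed; 3,000 runs) it gave 4.1 to 5.3%, while Fisher's test gave 4.5 to 9.3% at 0.1%, 6.9 to 36.8% at 1%, 18.2 to 64.5% at 5% and 28.0 to 76.4% at 10%.

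**6. Fewer PEP takers.** With 200 per cluster (an assumption), Fisher's simulated error in 5,000 runs was 3.6 / 4.5 / 7.8% at 1% risk, 5.2 / 9.2 / 21.3% at 5% and 6.4 / 14.8 / 34.5% at 10%.

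**The case against.** The strongest case is about size and consequence. Fisher's test does not exceed its nominal level by any material amount when AEs are rare, and the only field experience cited, PEOPLE with rifampicin alone, reports that "no adverse events were identified related to the study medication" (section 7.1.1). The figure of 1,708 rests on full-village coverage, which section 9.3.1 assumes for the first year only. Later rounds treat the zones around newly found cases and exclude people who received PEP in the past two years, so cluster denominators may be much smaller. The stated outcome is descriptive, and no decision rule uses the p-value. Pairs are matched on leprosy prevalence, which has no stated link to AE reporting, and an unpaired cluster t-test also held its level (4.3 to 5.7%). A phase 3 SAP could still add the missing detail.

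Most of this stands as a limit on size. The highest rates need common AEs, large clusters and marked village variation together. It does not rescue the method. The PEOPLE experience says nothing about bedaquiline, and sections 2.1.2 and 9.2.2 describe these reactions as potentially frequent. With 200 per cluster the error still reaches about 9% at 5% risk and CV 0.2. The choice between paired, unpaired and mixed-model analyses is a choice among methods that respect the design; Fisher's test on individuals is not one of them. A future SAP would have to depart from the protocol sentence.

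**Conclusion.** The concern holds. As written, the phase 3 AE comparison ignores the unit of randomization, and its p-values are too small whenever AE reporting varies by village and events are not rare. At 1,708 per cluster the simulated error of the nominal 5% test ranges from about 4% (0.1% risk, CV 0.1) to about 73% (10% risk, CV 0.4); at 1% risk it is about 7 to 31%. These figures rest on assumed AE risks and assumed village variation, and on one binary outcome per person. They do not model household clustering or repeat dosing, and they assume that pairing absorbs none of the village variation; if it does, Fisher's error would be lower.

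The matter should be fixed but is limited in reach. It concerns a secondary tolerability comparison and leaves the primary leprosy analysis unaffected. That clustering is ignored is certain; how much it will matter cannot be settled from the documents.

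**What to change.** In section 9.3.2, or in the phase 3 SAP with a matching protocol change, replace the Fisher sentence for phase 3 with: *Arms will be compared with a paired t-test on cluster-level AE proportions among PEP recipients over the 22 randomized pairs, and the difference will be reported with its cluster-based 95% confidence interval.* Keep Fisher's exact test for phase 2. A mixed model or GEE with village as cluster and a small-sample correction would also serve.

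The same text should settle three definitions. First, who counts as a recipient, since some people in BE-PEP villages receive SDR-PEP (sections 3.1 and 4.2). Second, how repeat rounds and second doses enter the proportion. Third, whether villages are weighted equally, as the unweighted t-test does.

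The cost is a sentence or two, slightly more programming and wider intervals. The width ratio is t(0.975, 21 df) × √DE / 1.96 = 2.080 × √DE / 1.96. For CV 0.1 to 0.4 this is about 1.1 to 1.2 at 0.1% AE risk, 1.1 to 2.1 at 1%, 1.5 to 4.2 at 5% and 1.8 to 5.9 at 10%. Power falls too: for 0.1% versus 0.2% with CV 0.1 to 0.2 and size CV 0.6 (all assumed), it was about 0.92 to 0.93 for Fisher's test and 0.78 to 0.79 for the paired t-test. The change corrects for clustering only; it does not remove reporting bias from open-label treatment.

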The BE-PEOPLE study is a follow-up to the ongoing PEOPLE study, in Comoros only. Baseline screening will take place in 2022 and the beginning of 2023, partially overlapping with the final screening round of PEOPLE. We will then re-randomize 34 out of 48 villages that were already part of PEOPLE as well as 10 new clusters to two new study arms: arm 1 in which BE-PEP i.e. bedaquiline (400 or 800 mg depending on weight band) combined with rifampicin (10 mg/kg) will be provided as post-exposure prophylaxis, and arm 2 in which only SDR-PEP (rifampicin 10 mg/kg) will be provided. Anyone living within 100 meters of an index case (PEP zone) will be eligible for PEP. In case 50% of the village population or more lives within 100 meters of an index case the PEP zone will be extended to the entire village. For the first PEP distribution at village level any leprosy case included in the study population detected during the annual village screening or in the preceding five-year period, i.e. since January 1st, 2018 will be considered an index case. The following years, any leprosy case detected after the last year's screening up to and including the village's screening round of the current year will be considered an index case.

Annual village screening rounds will take place for 4 years starting in 2023. When annual screening is completed in a village, a list of eligible households (based on the PEP zone) will be elaborated followed up with PEP intervention to those individually eligible based on annually evaluated inclusion and exclusion criteria listed in the protocol. If a participant whose village is randomized to the BE-PEP arm, is individually ineligible for BE-PEP, but individually eligible for SDR-PEP, the participant may receive

SDR-PEP. Because there has been no distribution of PEP during the final PEOPLE survey round in 2022, all participants will in principle be eligible again for PEP when the BE-PEOPLE intervention starts in 2023.

The final screening round will take place 4 years after the first screening round in 2023 and will in a subset of villages (those that belonged to arm 4 of PEOPLE) be followed by a serological survey (PGL-I) aimed at measuring prevalence of infection with *M. leprae*.

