1. Concurrent (within the last three week period before PEP administration) use of medication not present on the 'safe' list

Remarks regarding PEP distribution:

- Children between 2 and 5 years of age or weighing between 10 and 20 kg or people taking medication from the unsafe list will be excluded from BE-PEP and offered SDR-PEP if eligible.
- Study participants living in the PEP zone but ineligible for PEP due to the PEP inclusion or exclusion criteria or being absent during the village PEP distribution round will not be automatically included in the PEP distribution the following year. It is possible that a study participant is not eligible one year due to the PEP inclusion or exclusion criteria but will be eligible for PEP the next year when the household is again part of the newly calculated PEP zone and the individual inclusion or exclusion criteria are respected.
- Household contacts of an index case in the BE-PEP arm absent during the 1st annual PEP distribution but present during the 2nd annual PEP distribution will only be offered PEP once that year and will not be revisited after 30 days.
- Participants who are not BE-PEP eligible due to concomitant medication not present on the 'safe list' can be provided SDR-PEP, provided they do not meet any other exclusion criteria.
- Children who are not BE-PEP eligible solely for not meeting age and weight criteria, can be provided SDR-PEP if aged 2 years or above and weighing 10 kg or above.

All leprosy patients diagnosed during the study period, even those from non-study villages, will also be enrolled in a sub-study in which potentially a nasal/tongue swab, a tongue scraping sample, face mask sample and skin biopsies will be collected from non-facial lesions. qPCR on these samples will allow to verify the accuracy of the clinical diagnosis and further processing with Deeplex Myc-Lep V3 of qPCR positive samples (or WGS if needed), will allow to monitor drug resistance and assess the impact of the intervention on transmission of *M. leprae*. As drug resistance may also affect treatment for tuberculosis, we will also sample all GeneXpert positive tuberculosis patients identified on Anjouan, Mohéli, and Grande Comore during the study period for drug resistance testing with Deeplex Myc-TB XL, and verify whether they received rifampicin and/or bedaquiline in the past.

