To calculate the sample size required for the phase 3 trial, with the main objective of assessing the impact of BE-PEP versus SDR-PEP on leprosy risk at individual level, we used the methodology described by Hayes and Bennet for cluster randomized trials.(10) Our aim is to show a 50% reduction in risk of leprosy over a 3-year period for those that received BE-PEP (arm 1) compared to those that received SDR-PEP (arm 2). We assume that in the latter arm the risk over a 3-year period will be 0.0033, i.e. 1.1 per 1,000 per year. The mean population size of the villages targeted is 2,819, however children below 5 years of age or weighing below 20 kg are not eligible for BE-PEP and make up 27% of the population. Even though part of them will be eligible for SDR-PEP, we will exclude them from this analysis because the risk of leprosy varies with age. We will therefore only compare individuals aged 5 years or above and weighing 20 kg or above. We also took into account the participation rate, i.e. the proportion of eligible participants that agreed to take PEP, which in the PEOPLE trial was 83%. Thus on a population of 2,850, only 1,708 will effectively be available for analysis. For the PEOPLE trial we calculated a coefficient of variation between clusters (km) of 0.34, in the BE-PEOPLE trial we assume a slightly higher Km, 0.4. To achieve a power (1- β) of 90% with an average cluster size of 1,708 and $\alpha = 0.05$, 22 clusters per study arm would be required, i.e. 75,152 subjects for the two arms combined. To enroll 75,152 eligible subjects we need to target a population of approximately 124,000 in total. We therefore selected 43 villages with a total population of 124,035, of which one will be divided into two clusters.

Of the 43 villages selected, 34 are already enrolled in the PEOPLE trial with a total population of approximately 73,000. In addition we have selected 9 new villages with an estimated available population of 51,000. For the new villages we have assumed a coverage of 50% only as they are large villages and we will exclude the neighborhoods from which leprosy patients are seldom reported.

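### Phase 3 adverse events are to be compared between village arms, although arm 1 includes people given rifampicin only, so the comparison does not isolate what BE-PEP adds

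*Protocol*

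**What the plan says.** Protocol section 2.2.2, objective 2, defines the phase 3 adverse event outcome by regimen taken: "The proportion of participants treated with BE-PEP that report adverse events, with a breakdown by type of event". It names no comparator. Section 9.3.2 tabulates the prespecified events and adds a test: "Comparisons between study arms will be done using" Fisher's exact test.

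Arms are villages, and arm 1 contains SDR-PEP recipients by design. Section 3.1 says that if someone in a BE-PEP village "is individually ineligible for BE-PEP, but individually eligible for SDR-PEP, the participant may receive" SDR-PEP. Section 4.2 names two such groups:

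- By age or weight: "Children who are not BE-PEP eligible solely for not meeting age and weight criteria, can be provided SDR-PEP", from age 2 and 10 kg upwards.
- By medication: "people taking medication from the unsafe list will be excluded from BE-PEP and offered SDR-PEP if eligible".

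Section 4.3 gives the share of people below the age or weight limits: they are "not eligible for BE-PEP and make up 27% of the population".

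Section 7.2.3 has everyone who took PEP, on either regimen, asked about adverse events. Section 9.1 makes intention to treat the primary phase 3 approach. Section 9.3.1 models type of PEP for the efficacy analysis and leaves out non-recipients and those below the BE-PEP limits. Section 9.3.2 does not carry that restriction over to adverse events. The SAP analyses safety by treatment administered (section 5.1), but it covers phase 2 only.

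**The concern.** On the wording of 9.3.2, the arm 1 adverse event proportion pools BE-PEP and rifampicin-only recipients, and both arms include young children who would never be given bedaquiline. The arm 1 figure in the comparison would then differ from the proportion reported for objective 2.

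The phase 3 schedule (Table 3) contains no ECG or liver test, so this is the main planned between-arm safety comparison of the phase. Section 7.2.3 classes a list of common events within 24 hours as related to PEP in either arm. Causality coding therefore cannot separate what bedaquiline adds; only a like-for-like comparison of regimens can. Section 3.1 gives selection bias no role here, but the design summary there removes under-limit children from the efficacy comparison for that reason, and it applies equally to adverse events.

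**Working it through.** **Inputs.** From section 4.3: mean village population 2,819; 27% below the BE-PEP limits; uptake 83%; 22 clusters per arm; about 124,000 people in total, so 62,000 per arm. Not given: the share s of the 27% who qualify for SDR-PEP (the 27% includes children under 2 years or 10 kg, who get no PEP), the share on off-list medication, the share of household contacts, and any adverse event rate.

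**The plan's own figure.** 2,819 × 0.73 × 0.83 = 1,708 per cluster, and 1,708 × 44 = 75,152. Both match section 4.3, so the 27% and 83% are used there as they are here. No figure is stated for the adverse event comparison.

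**Dilution among dosed people.** Let f be the rifampicin-only share of dosed people in arm 1. Their counterparts in arm 2 also take rifampicin only, so on average they contribute equally to both arms and cancel:

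arm difference = (1 − f) × (BE-PEP risk − SDR-PEP risk).

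With equal uptake, and counting age and weight only, f = 0.27s / (0.73 + 0.27s). The counts below are 62,000 × 0.83 × 0.27s, set against 62,000 × 0.83 × 0.73 = 37,566 BE-PEP recipients. They assume that everyone lives in the PEP zone. The last column uses assumed rates of 2% (SDR-PEP) and 4% (BE-PEP), a true difference of 2.0 points.

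| s (assumed) | f | Kept, 1 − f | Rifampicin-only in arm 1 | Arm difference (points) |
|---|---|---|---|---|
| 0.4 | 0.108/0.838 = 12.9% | 87.1% | 5,558 | 1.74 |
| 0.6 | 0.162/0.892 = 18.2% | 81.8% | 8,337 | 1.64 |
| 0.8 | 0.216/0.946 = 22.8% | 77.2% | 11,115 | 1.54 |
| 1.0 (ceiling) | 27.0% | 73.0% | 13,894 | 1.46 |

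Off-list medication would add to f. If all enrolled people formed the denominator, BE-PEP takers would be 0.73 × 0.83 = 60.6% of arm 1, and about 61% of the difference would be kept.

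**Risk ratio.** This also depends on the rate in the rifampicin-only group. At f = 0.20 with 2% and 4%, the arm risk ratio is 2.00, 1.89, 1.80 or 1.67 if that group's rate is 0%, 1%, 2% or 4%. No single risk ratio can be quoted.

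**Second dose.** Suppose a share h of BE-PEP recipients are household contacts who take two doses, with independent 4% risks. Their risk of any event is 1 − 0.96² = 7.84%. At f = 0.20 the per-person arm difference is 0.8 × (2.0 + 3.84h) points:

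- h = 0: 1.60
- h = 0.10: 1.91
- h = 0.20: 2.21

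It equals the per-dose difference of 2.0 points at h = 0.5/3.84 = 13%. So the by-arm figure can fall below or above the per-dose difference.

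**Effect on power (illustrative).** With assumed rates of 1.0% and 1.2%, 22 × 1,708 = 37,576 eligible recipients per arm, two-sided 5% and no allowance for clustering, power is 75% for the restricted comparison. By arm it is 66% at f = 0.20 and 62% at f = 0.27.

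**The case against.** Comparing arms as randomized follows section 9.1. Objective 2 asks only for a descriptive proportion, which is undiluted and stands whatever the test does. Section 9 leaves detail to a SAP, and the phase 2 SAP shows that the sponsor analyses safety by treatment administered. With tens of thousands dosed per arm, a large excess would be detected either way, and the DSMB reviews adverse event follow-up during phase 3.

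Much of this stands, and it limits the consequences: harm is not hidden from oversight, and only small excesses lose noticeable power. It does not settle the population. The SAP's rule does not reach phase 3. Section 9.3.1 names type of PEP where regimen is meant, whereas the village-level analysis in 9.3.2 uses arms for whole villages.

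A reader might go further and infer that the arm comparison necessarily understates bedaquiline's harm. The documents do not support that. Table 3 and its notes give arm 1 household contacts a second dose and a second adverse event visit that arm 2 does not have, which raises the arm 1 per-person proportion.

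Nor would it be clean simply to set BE-PEP recipients against age- and weight-eligible SDR-PEP recipients in arm 2. Off-list medication users would then leave arm 1 only. If they report more events, that contrast would itself understate the bedaquiline excess.

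**Conclusion.** The point holds as a mismatch between outcome and comparison. Section 9.3.2 as worded compares mixtures of regimens, and nothing in the documents defines a phase 3 safety population that would prevent this. Per dose and among dosed people, the comparison keeps 1 − f of the risk difference. This is 77–87% if 40–80% of those below the limits qualify for SDR-PEP at equal uptake, and 73% at the ceiling from age and weight alone. These sizes rest on an assumed s; the documents do not give f or any adverse event rate. The net direction on a per-person count is not established, because the second dose works against the dilution. The comparison should be redefined before phase 3 safety data are analysed.

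**What to change.** In section 9.3.2 and in the phase 3 SAP:

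1. Restrict the adverse event comparison in both arms to PEP recipients who meet the BE-PEP age and weight limits, as the primary analysis already does.
2. Compare events after the first dose, and tabulate second-dose events separately.
3. Present results by regimen received, and tabulate recipients below the limits separately by arm.
4. State how off-list medication users are handled. Either keep them in both arms, in a by-arm comparison of age- and weight-eligible recipients (which leaves a small dilution from this group), or compare BE-PEP with SDR-PEP recipients and say openly that they are removed from arm 1 only, unless off-list use is also recorded in arm 2.

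Items 1 to 3 cost a few sentences: dose, eligibility criteria and adverse events are already entered in the study database (sections 6.2 and 11.1). Removing off-list users from both arms may need extra data collection. Section 4.2 applies the medication criterion to BE-PEP only, and section 11.1 lists concomitant medication as a phase 2 item. The statistical downside is that low-weight recipients leave the between-arm test and are only described.
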